## 9.5 Data collection schedule for study staff.

### 9.5.1 For the AYA and caregiver survey schedules for both the run in and RCT, please see

Figures 3A and 3B. Medical record data will be collected at baseline and monthly until the 3-month mark in both the run in and RCT. Additional medical record abstraction will occur for the RCT at 6-, 9, and 12-months. The caregiver to complete the surveys will be designated at enrollment. RA's at each site will prospectively abstract information from the medical record using a study-specific case report form (CRF) adapted from prior studies. This will include: (1) AYA participation in goals of care conversations: dates of documented conversations with medical team regarding prognosis, treatment decisions, and/or goals of care, whether or not AYA was present, and if there is documented active AYA participation. (2) Benchmarks of Palliative Care Utilization: number and frequency of documented psychosocial and palliative care referrals and meetings, hospice referrals, limitation-of-resuscitation orders, completion of advance care planning documents, and end of life details (i.e. location of death, clinical involvement and family support (sibling & financial assessments)). (3) Clinical covariates: the AYA's diagnosis, cancer/tumor-directed treatments, and intensity in the past month, number of and reason for hospital days

(anticipated and unanticipated), prescription psychiatric and/or mood altering medications, prescription opioids and other pain medications, and number of documented palliative care/psychosocial encounters. These variables were selected based on prior evidence that child well-being and family psychosocial needs affect immediate psychosocial outcome metrics (e.g., psychological distress and quality of life).

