**1. Objectives**

**1.1 Overview.** Among patients with cancer and their families, early integration of palliative care may improve quality of life. This is particularly important for Adolescents and Young Adults (AYAs) because their distinct developmental challenges related to identity, relationships, and vocation may add to the burden of cancer. Among AYAs with advanced cancer, most understand that they may die and report that discussing end-of-life preferences, goals, and fears would be helpful; however, only 53% engage in such conversations. While national guidelines call for integrated palliative care in AYA oncology, developmentally targeted, evidence-based interventions designed to meet psychosocial and communication needs are lacking.

A potential barrier to improving the experiences of AYAs with advanced cancer may be their limited opportunities to develop “resilience resources” such as stress-management, goal-setting, positive reframing, and meaning-making skills. These resources may mitigate negative outcomes, facilitate engagement in goals of care discussions, and improve quality of life. Furthermore, promoting these resources among AYAs may give them the tools to more successfully navigate the challenges of the cancer experience.

Our research program is built on the central hypothesis that promoting resilience resources will improve psychosocial well-being. Over a series of studies, we developed a conceptual framework of resilience in pediatric cancer, affirmed associations between resilience resources and outcomes, and developed a novel resilience resources intervention (Promoting Resilience in Stress Management, PRISM). PRISM is a manualized, skills-based training program comprised of four 30-60 minute, in-person, one-on-one sessions plus a facilitated parent/caregiver/spouse/significant other family-meeting.

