**1.2.3.4 Evaluate the impact of PRISM-AC on parent distress.**

**1.2.3.4.1 Outcome Measures:** parent anxiety (Generalized Anxiety Disorder Screener, GAD-7), depression (PHQ-8), and HRQOL (SF-36), 3-months post-enrollment.

**1.2.3.4.2 Hypothesis:** Parents of PRISM-AYAs will report lower anxiety and depression, and better HRQOL compared to parents of AYAs in usual care.

**1.2.3.4.3 Exploratory Outcome:** Family Experience (selected items from Hospital Consumer Assessment of Healthcare Providers and Systems [HCAHPS] survey).

**1.2.3.5** Evaluate the impact of PRISM-AC on family “palliative care activation.”

**1.2.3.5.1 Outcome measures:** (a) AYA- and parent- perceptions of AYA involvement in Decision-Making, measured with the Decision-Making Involvement Scale; (b) medical record documented goals of care conversations; and, (c) medical record documented AYA utilization of formal palliative care and other psychosocial services, hospice, limitation of intervention orders, and other advance care plans.

**1.2.3.5.2 Hypothesis:** PRISM families will demonstrate higher levels of activation compared to usual care.

**1.2.3.6** Explore longitudinal impact of PRISM-AC on above outcomes at 6-, 9-, and 12-months following enrollment.

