### **1.3 Rationale for the Selection of Outcome Measures**

Palliative Care interventions aim to alleviate suffering and improve HRQOL. Hence, we selected HRQOL as our primary outcome, with additional clinically relevant patient-centered outcomes including symptom burden and psychological symptoms as our secondary outcomes.

Patient outcomes are not the only ones of import in pediatric, adolescent, and young adult populations. Indeed, patient and parent outcomes are inextricably linked. Parent psychological distress is highly prevalent among children with advanced cancer, and it is associated with perceived child suffering and quality of family communication. Hence, we elected to determine if a patient-centered intervention could also improve parent outcomes.

Regarding palliative care utilization, traditional measures focus on the circumstances of death (e.g., chemotherapy within the last 30 days, advance care planning documentation). These metrics are less relevant in pediatric and AYA populations. AYA advanced cancer may last years. Content and AYA participation in goals of care discussions evolve. Low-intensity palliative chemotherapy may improve quality of life. And, AYAs defer to their parents for medical decision-making, suggesting formal advance care planning documents incompletely represent AYA perspectives. For these reasons, pediatric palliative care research has shifted towards outcomes of patient/family engagement and activation. Activation is defined as the extension of self-efficacy into self-management. It implies knowledge and confidence to take action, actively change behaviors, and maintain changes over time. It may be more representative of evolving pediatric and AYA palliative care involvement. Importantly, higher activation is associated with improved psychological wellbeing and HRQOL among adults with chronic illness, and with medication-adherence and clinical outcomes in pediatric settings. Hence, we selected global activation as a measure of palliative care utilization in this study.

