### **3.2 Eligibility Criteria:**

#### **3.2.1 Inclusion Criteria FOR AYA PATIENTS (RCT & Run in)**

- 3.2.1.1 Age 12-24 years
- 3.2.1.2 Patient aged 12-17 years: has signed informed assent and their parent/legal guardian has signed informed consent for study participation.
- 3.2.1.3 Patient aged 18-24 years: has signed informed consent for study participation.
- 3.2.1.4 Diagnosed with advanced cancer (progressive, recurrent, refractory disease, or any diagnosis associated with <50% survival), or any other progressive/recurrent brain or solid tumor, at least 2 weeks prior to enrollment.
- 3.2.1.5 Receiving care at Seattle Children's Hospital (SCH), Texas Children's Hospital/Baylor College of Medicine (BCM), Children's Hospital Los Angeles (CHLA), or University of Pittsburgh Medical Center Children's Hospital (UPMC)
- 3.2.1.6 Able to speak English language (for PRISM sessions)
- 3.2.1.7 Able to read English or Spanish language (for completion of surveys)
- 3.2.1.8 Cognitively able to participate in interactive interviews, PRISM sessions, and survey completion, as deemed by medical staff.

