## 8.0 Study Endpoints

**8.1.1 Primary Endpoint: 3-month follow-up of last AYA participant including patient-reported outcome survey completion.**

**8.1.2 Secondary Endpoints:**

8.1.2.1 3-month follow-up of last parent participant including parent-reported outcome survey completion.

8.1.2.2 3-month data collection of “palliative care activation” measures, including surveys, medical record data extraction.

8.1.2.3 12-month follow-up of last participant for exploratory cohort.

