### 11.5.3 Secondary Outcomes

**11.5.3.1** The goal for parent outcomes is to evaluate the effect of the intervention on *parent psychological distress* and HRQOL. Mean total scores from each parent instrument at 12 weeks will be the secondary outcomes of interest. We will model distress and HRQOL separately and follow a similar approach to the analyses for continuous outcome measures in Aim 1. As sex and baseline patient HRQOL may be predictors of these outcomes, each will be included if imbalanced between arms.

**11.5.3.2** To compare patient and caregiver *activation*, we will measure patterns in multiple domains: AYA- and parent-reported Decision-Making Involvement Scores, AYA participation in goals of care conversations, and formal palliative care service utilization including documented referrals for hospice and charted decisions to limit resuscitative efforts. For all outcomes, results between trial groups will be compared using analysis of variance with trial group as the factor of interest. We will explore whether change in activation scores are correlated within families and/or modified by parent/child characteristics (sex, psychological distress scores, cancer/tumor-type, among others) using ordinal logistic regression models with cumulative logits, where change activation level is categorized as negative, null, or positive.

**11.5.3.3 Exploratory analyses** will evaluate prospective and longitudinal survey and clinical data beyond month 3 (primary endpoint) at months 6, 9, and 12 of the study. Comparisons between groups will still use an intention to treat approach as described above. Additionally, we will explore the relationship between biomedical variables and patient reported anxiety and depression through a combination of paired and unpaired t-tests, chi-squared (or Fisher's exact) tests, and linear and logistics regression. HRV will be measured in 24-hour increments using both time and frequency domain parameters as established by the international Cardiology task force

guidelines. Means and standard deviations will be compared to published normative data in adolescents.

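### The plan does not say whether chart events before randomization count toward palliative care activation, and the arm comparison does not use the baseline chart abstraction.

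*Combined protocol and SAP*

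**What the plan says.** Activation is a secondary aim with a directional hypothesis. Section 1.2.3.5.1 defines it by the Decision-Making Involvement Scale (DMIS), documented goals of care conversations, and "medical record documented AYA utilization of formal palliative care and other psychosocial services, hospice, limitation of intervention orders, and other advance care plans". No start date is attached to these events. Section 8.1.2.2 sets the endpoint at 3 months for activation "measures, including surveys, medical record data extraction", again without a window.

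On collection, Section 9.5.1 states "Medical record data will be collected at baseline and monthly until the 3-month mark", with further abstraction in the RCT at 6, 9 and 12 months. It lists the utilization benchmarks as "number and frequency of documented psychosocial and palliative care referrals and meetings, hospice referrals, limitation-of-resuscitation orders, completion of advance care planning documents". Dates are named only for goals of care conversations. Abstraction is described as prospective.

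On analysis, Section 11.5.3.2 says that for all activation outcomes "results between trial groups will be compared using analysis of variance with trial group as the factor of interest". Section 11.5.1 adds adjustment for site, age and any baseline characteristic that is clearly imbalanced. Change in activation appears only in an exploratory ordinal model. For the primary outcome, by contrast, Section 11.5.2 makes the baseline score a covariate.

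On entry, Section 3.2.1.4 requires the qualifying diagnosis "at least 2 weeks prior to enrollment" and sets no maximum. Section 3.2.2 does not exclude prior palliative care, hospice referral, resuscitation limits or advance care plans. Section 1.3 notes that "AYA advanced cancer may last years".

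**The concern.** An AYA who already has a hospice referral or a completed planning document at enrollment cannot acquire a first one because of PRISM. If that AYA is scored as activated, the same constant enters both arms and the contrast for the item shrinks. The imbalance rule does not guard against this: a prior event that is evenly spread between the arms triggers no adjustment, yet it still dilutes an ever/never contrast.

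The text lets two analysts count differently and both be following the plan. If the window is chosen after the data are seen, the choice is post hoc. If prior events are included, a null result could not separate no effect from nothing left to change. The baseline chart data that would settle this are already being collected.

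**Working it through.** **The plan's own figure.** No power or event rate is stated for any activation outcome. The nearest stated figure is the primary design in Section 11.3.1.1: 72 per arm, difference 8.1, SD 17.2, 5% type I error (taken as two-sided). The standard error is 17.2 × √(2/72) = 2.867, and power = Φ(8.1/2.867 − 1.96) = 80.7% (80.1% with the noncentral t). Attrition: 144/(1 − 0.26) = 195. Both reproduce. They supply the 72 per arm used below and do not otherwise bear on the point.

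**Ever/never items.** Let p0 be the share with the event at baseline and q the 3-month risk of a new event among the rest. Then

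- ever charted by month 3 = p0 + (1 − p0)q
- arm difference = (1 − p0)(q_PRISM − q_control)

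Analysis of variance on a 0/1 item compares these proportions. The alternative compares q directly, with 72(1 − p0) AYAs per arm at risk.

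Power = Φ[(d − 1.96·se0)/se1], where d is the arm difference, se0 is the pooled standard error and se1 the unpooled one.

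Assumptions not in the documents: q = 20% versus 40%, and each value of p0.

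Worked case, p0 = 20%:
- Ever charted: 0.36 versus 0.52, d = 0.16, se0 = 0.0827, se1 = 0.0816. Power = Φ[(0.16 − 0.1621)/0.0816] ≈ 49%.
- New events: 57.6 at risk per arm, d = 0.20, se0 = 0.0854, se1 = 0.0833. Power = Φ[(0.20 − 0.1674)/0.0833] ≈ 65%.

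| p0 | Difference, ever charted | Power, ever charted | Power, new events among event-free |
|---|---|---|---|
| 0% | 20 points | 75% | 75% |
| 5% | 19 points | 68% | 73% |
| 10% | 18 points | 61% | 70% |
| 20% | 16 points | 49% | 65% |
| 30% | 14 points | 39% | 59% |
| 50% | 10 points | 24% | 46% |

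With q = 10% versus 25% and p0 = 30%, the two powers are 25% and 51%. Chart outcomes need no completed survey, so more than 72 per arm may contribute. With the 98 per arm randomized, q = 20% versus 40% and p0 = 20%, they are 62% and 79%.

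**Counts.** Events before randomization have the same expected number in both arms, so they cancel from the expected mean difference and only the variance grows. As an illustration, assume a true difference of 1 event, a post-randomization SD of 2 and 72 per arm: power is 85%. Adding an independent pre-enrollment component with SD 2 gives a total SD of √(4 + 4) = 2.83, and power falls to 56%.

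**The case against.** The strongest reply is that no passage says earlier events count. A reader might infer from the open definitions that they do, and that activation is therefore diluted. The documents do not support that. Prospective abstraction, with a baseline round and separate monthly rounds, fits counting only follow-up events at least as well, and the study-specific case report form may carry its own look-back rule. This stands: the defect is an unstated window combined with unused baseline data.

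A reader might also infer that many AYAs arrive with these events. Eligibility shows that this is possible, not how often it happens. Section 2.1.1 describes late palliative referral and delayed advance care planning, which points to low prevalence for the once-only items. At 5% prevalence the loss is small (68% against 73%).

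It is tempting to take the statement in Section 1.1 that "only 53% engage in such conversations" as a baseline prevalence. It concerns end-of-life conversations, which are repeated events rather than once-only ones, and is not given as a charted rate at enrollment. It is not used here.

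Nor does the comparison rest on trial group alone, since age, site and clear imbalances are adjusted for. The benchmarks are worded as number and frequency, and for counts only precision is lost. Randomization balances prior events on average, so this is not bias toward either arm.

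What the reply leaves untouched is that the stated comparison makes no use of each AYA's baseline chart status, although it is collected and would sharpen the comparison.

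**Conclusion.** The point holds as a cheap improvement to a secondary aim. The plan gives no counting window and no at-risk set for chart-based activation, and its arm comparison does not use the baseline abstraction. If prior events are included, ever/never items lose the fraction p0 of their risk difference and counts lose precision. The shrinkage factor is exact when the prevalence and the new-event risks are as defined above. The power figures are illustrations, because prevalence and event rates are assumed: about 61% versus 70% at 10% prevalence, 49% versus 65% at 20%, and 24% versus 46% at 50%. The primary PedsQL analysis is unaffected. So is the DMIS, which asks about a conversation in the past month.

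**What to change.** In Sections 9.5.1 and 11.5.3.2:

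- State that chart outcomes are counted from randomization to month 3.
- For repeated events (conversations, meetings, encounters), compare post-randomization counts with the baseline count as a covariate.
- For once-only events (first palliative care or hospice referral, resuscitation limit, completed advance care document), compare new events among AYAs without that event at baseline.
- Place events by the baseline and monthly abstractions, or add a date field for items other than goals of care conversations, the only ones for which dates are now specified.

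The cost is a few sentences and possibly a small addition to the case report form. The downside is that fewer AYAs contribute to each once-only item. In every case calculated with a prevalence above zero, the new-event comparison still had more power.

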Because PRISM sessions 1-4 build skills to identify goals and values, VMC is an appropriate culmination of skills and offers concrete examples of how to utilize them. For this reason, PRISM-AC will introduce specific VMC pages (see appendix) as examples of how such skills might be helpful in cases of advanced cancer and progressive/recurrent tumors, and then offer opportunities to practice them in real time. Interventionists will only complete up to four specific pages with AYAs: page 4 "My Comfort", page 5 "My support", page 8 "My Friends and Family to Know", and page 9 "My Spiritual Thoughts". If AYAs express a desire to do any of the other pages, we will redirect them to their medical team, social work, and/or their parents. Specifically, we will introduce the VMC booklet and then highlight the pages and allow participants to choose the one(s) that resonate with them "a la carte" (see appendix). Although advance care planning includes sensitive topics like end-of-life planning, this booklet was selected specifically because they are more generic and applicable to all AYAs with illness. If an AYA has no specific preferences, the interventionist will direct the patient to the page about "my comfort" (VMC page 4) and complete that page during the session.

Introductory scripts were approved by VMC developers and are provided in the Voicing My Choices Session appendix document. Following the completion of VMC pages during the PRISM-AC session 5, AYAs will keep their booklet and have opportunities to continue exercises on their own, with family, with study staff during return visits (see “boosters” below), or with medical staff, as appropriate and/or desired. Again, interventionists will only do the four selected pages with the AYA and will redirect as appropriate if the AYA wishes to complete other pages. Finally, at the close of the fifth session, AYAs will be given a checklist of all the skills and topics covered throughout PRISM-AC, including VMC content. Staff will ask what they would like to share with their parent(s), spouses, significant others, or guardians during the final session (see “coming together” below) such that the interventionists can prepare to facilitate the final session.

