In the event of other concerns from interventionists and/or other study staff based on interactions with AYAs and families, as well as in other cases of concern for patient or others' safety, the same processes will occur, including immediate referrals to the site PI, and the patients' primary medical and social work teams for in-person evaluation or referral to the appropriate mental health professional if warranted. After hours, the site PI and on-call providers from the medical teams will be notified. All study-related concerns for patient or other person's safety will be reported as an adverse event (AE) to the IRB and Data Safety Monitoring Committee (DSMC, see "Data Safety Monitoring Plan"), within 1 week of study staff awareness. In addition, the PI will review the potential risks and reported findings at least once monthly with study staff from all participating sites. While this is not a pharmacologic

trial and we do not anticipate medical complications, sites will nevertheless notify the IRB and DSMC of all participant deaths at the time of study renewal (annually). Unanticipated (non-medical) participant deaths will be reported to the DSMC within 1 week with a determination if the event might be attributable to the study. In such cases, the DSMC chair may convene the committee and/or suspend the study for additional review (see section 13.5 below).

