**13.6.4 Identification, review and report of adverse events and unanticipated problem.**

Adverse events information will be collected at all assessment points and recorded on standard forms. We will collect information on all potential types of adverse events. Consistent with NIH and the sites IRBs policies, adverse events will be promptly reported in writing to the NIH, individual IRBs, and the DSMC chair. The DSMC will modify or stop the study if any such complaints represent a legitimate concern about the study procedures or methods.

**13.6.5 Compliance with monitoring requirements.** Compliance with the monitoring plan will be ensured through the Lead RA's close supervision. The Lead RA will hold no less than monthly calls with the sites to monitor recruitment and protocol adherence. Site RAs will gather required information on an ongoing basis and send monthly written reports to Lead RA. The Lead RA will schedule yearly on-site monitoring visits as the coordinating site for data completeness and accuracy. Site RAs will assist in providing on-site monitors with appropriate access to all study related charts and databases during the visit.**13.6.6 Assessment of relevant external factors.** Given the characteristics of the intervention, it is unlikely that a breakthrough result from another study will change the course of this study.**13.6.7 Interim analysis plan.** A primary endpoint interim analysis to assess for safety and missingness will be led by the study statistician after half of the targeted sample size of participants have reached the primary endpoint. The DSMC will determine a priori stopping occurrence of serious events, including (but not limited to) stopping the study for efficacy if interim analysis is significant. For efficacy endpoint, if an effect were found, the DSMC will be presented with unblinded results (i.e. they will be able to ascertain which results correspond to the intervention arm). Based on these results, the DSMC will present recommendations to the study team regarding early stopping or continuation of the trial. There are no pre-planned stopping rules for adverse events since these are not anticipated.**14.0 Withdrawal of Subjects****14.1 Plan for Non-Responders**

Response to the intervention will be determined upon study completion (not in “real-time.”). All participants, including those on the intervention arm, will continue to receive usual care, including as-needed referrals for professional psychology services.

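### The chart-based referral count in the secondary activation outcome includes referrals that study staff start themselves, and only the PRISM arm has scheduled session and booster contacts up to month 3

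*Combined protocol and SAP*

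**What the plan says.** Section 1.2.3.5.1 makes "medical record documented AYA utilization of formal palliative care and other psychosocial services" part of the palliative care activation outcome, together with Decision-Making Involvement scores and documented goals-of-care conversations. The hypothesis in 1.2.3.5.2 is that "PRISM families will demonstrate higher levels of activation compared to usual care". Section 8.1.2.2 sets the assessment at 3 months.

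Section 9.5.1 lists what is abstracted from the chart, including the "number and frequency of documented psychosocial and palliative care referrals and meetings". The same section also lists the "number of documented palliative care/psychosocial encounters" among clinical covariates. Neither item is described with a source for the referral.

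Section 13.3 starts a referral pathway "In the event of other concerns from interventionists and/or other study staff based on interactions with AYAs and families". The matter goes to the site PI and to the patient's medical and social work teams "for in-person evaluation or referral to the appropriate mental health professional if warranted". Study-related safety concerns are also reported as adverse events. Section 15.0 trains interventionists to alert those teams if thoughts of self-harm or harm to others are voiced.

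In session 5, an AYA who wants pages of the planning booklet beyond the four selected ones is handled as follows (9.4): "we will redirect them to their medical team, social work, and/or their parents".

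As background, section 14.1 says that all participants "will continue to receive usual care, including as-needed referrals for professional psychology services".

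**The concern.** Section 1.3 describes activation as self-efficacy carried into self-management, with the knowledge and confidence to act. A referral made because an interventionist heard something worrying and followed the safety procedure is a different event, but once charted it enters the same count.

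The opportunity for such events differs by arm. Sessions and every-other-week boosters up to month 3 belong to PRISM only. Controls are surveyed at baseline, before randomization, and at week 12, and their check-in visits accompany the abbreviated surveys at months 6, 9 and 12 (9.6). The difference in contact therefore falls inside the 3-month window.

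At stake is how a positive result on this component can be read. Without the source of each referral, a higher PRISM count could not be divided between families seeking services and study staff following safety procedures. Some of the same events would also appear in the adverse-event listing.

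**Working it through.** **Plan's figures.** The documents give no power or effect figure for activation. The sample size supplies n: 144 / (1 − 0.26) = 194.6, so 195 randomized, about 98 per arm (11.3.1.1). I use 98 because chart abstraction does not depend on survey return, and show 72 per arm as a check.

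**Scheduled PRISM contacts by week 12.** There are five main sessions plus the family meeting.
- Every two weeks (9.3.2.2): weeks 1, 3, 5, 7, 9, 11, so 6 contacts.
- Weekly (lower end of the spacing in the Table 1 note): weeks 1 to 6, then boosters at weeks 8, 10 and 12, so 9 contacts.
- Controls: no session or booster contacts.

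**Share of PRISM participants with at least one staff-started referral.** The rate per contact, r, is an assumption. The share is 1 − (1 − r)^k.

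| r | k = 6 | k = 9 |
|---|---|---|
| 0.5% | 3.0% | 4.4% |
| 1% | 5.9% | 8.6% |
| 2% | 11.4% | 16.6% |

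I carry forward 6% and 12% as illustrative added shares, a.

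**False-positive rate for any referral, with no true effect on activation.** Let p0 be the assumed background share in both arms and p1 = p0 + (1 − p0)a the share in PRISM. The test is a two-sided 5% two-proportion z-test with pooled null variance, both tails counted.

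Worked case, p0 = 0.20, a = 0.06, n = 98:
- p1 = 0.248, difference 0.048, pooled proportion 0.224.
- Null SE = √(2 × 0.224 × 0.776 / 98) = 0.0596.
- Alternative SE = √((0.160 + 0.1865) / 98) = 0.0595.
- Upper tail: Φ((0.048 − 1.96 × 0.0596) / 0.0595) = 0.124. Lower tail: 0.003. Total about 0.127.

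| Background p0 | a = 6% | a = 12% |
|---|---|---|
| 20% | 13% | 34% |
| 50% | 7% | 13% |
| 70% | 6% | 9% |

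At 72 per arm the same formula gives 11% and 26% at 20% background, and 6% and 11% at 50%.

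**Counts.** Section 9.5.1 collects counts and 11.5.3.2 specifies analysis of variance, so a simulation is closer to the plan: 72 per arm, Poisson background, 20,000 runs per setting, and a share q of PRISM participants with one extra referral. For q = 5%, 10% and 20%, rejection is 7%, 13% and 35% at a background mean of 0.5, and 5%, 7% and 13% at a mean of 2.0. With q = 0 it is about 5%.

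The inflation is thus appreciable when background use is uncommon and small when it is common.

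**The case against.** Several counter-arguments have force.

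- **Link to the tested outcome.** Section 11.5.3.2 names hospice referrals and decisions limiting resuscitation under palliative care utilization. It neither names nor excludes psychosocial referrals. Their inclusion rests on 1.2.3.5.1 and 9.5.1. This stands as an uncertainty.
- **The form itself is not in the documents.** Section 9.5.1 is a summary, so a source field may already exist. This also stands.
- **Narrow triggers.** Staff alert existing clinical teams, and mental-health referral follows only if warranted. The training in 15.0 concerns self-harm or harm to others. A reader might infer that anxiety cases on the HADS would drive referrals, but no section makes a HADS score a trigger.
- **Contact in both arms.** Section 13.3 covers any staff interaction, and the 72-hour survey review applies to everyone. A reader might infer that controls have no staff contact. They do (allocation, reminders, optional HRV monitoring in Seattle); what they lack is sessions and boosters. Six contacts is also not a floor, since modules may be combined, the family meeting skipped and boosters sent by email (9.4).
- **Session 5 redirects.** These may be an intended effect: 9.4 gives as an aim finding out whether session 5 enables such discussions. Nothing says that a redirect produces a charted referral.
- **Removing staff-started referrals from the main comparison.** A reader might see this as the natural remedy. It would depend on attribution after randomization by unblinded staff, almost only in PRISM, and some of those referrals would have happened anyway. It would depart from intention-to-treat and could penalise PRISM.

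None of this removes the core point: the described count combines two kinds of event, and one has more scheduled opportunity in PRISM.

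**Conclusion.** The point holds as a limited, optional one. The referral and meeting part of a secondary outcome can rise in PRISM partly through study-staff safety actions, and the described abstraction would not show how much. The bias matters only if such referrals occur and are charted, and neither frequency is given. On the assumed rates above, the false-positive rate at 98 per arm runs from about 6% to 34%, with the lower values where background psychosocial use is common.

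A reader might go further and infer that distress in the PRISM arm is scored as benefit. The documents do not support that. Distress is measured separately with the HADS, safety concerns are reported as adverse events, 11.5.3.2 defines no composite benefit score, and not every staff-started referral reflects distress. The Decision-Making Involvement Scale, the primary PedsQL outcome and the sample size are unaffected.

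**What to change.** Add one case-report-form field, if not already present, for who started each psychosocial, mental-health or palliative referral: study staff under 13.3 or 15.0, session 5 redirect, or clinical team or family.

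In 11.5.3.2:
1. State whether psychosocial referrals and meetings are part of the tested outcome.
2. Keep the all-referrals intention-to-treat comparison as the main analysis.
3. Report counts by source and arm.
4. Prespecify a sensitivity analysis that excludes safety-triggered study-staff referrals and the first meeting resulting from each. Show session 5 redirects separately.
5. Require any claim of higher activation on this component to say whether it holds in that sensitivity analysis.

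The cost is one field, a few sentences and a little extra logging. Session 5 redirects may need a new log entry, since no section requires them to be recorded. Source attribution would be unblinded, which is why it belongs in a sensitivity analysis. No safety procedure or referral practice changes.
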